### **3.1. Baseline**

For safety and efficacy endpoints, baseline will be defined as the last measurement prior to or on the date of first dose date in PTC743-CNS-005-LSEP.

### **3.2. Missing Data Handling**

All analyses will be based on observed data only, and no missing values will be imputed unless otherwise indicated.

### **3.3. Changes of Analysis from Protocol**

Although summaries for exploratory endpoints were included in the protocol, these endpoints will only be listed.

## 4. SUBJECT DATA

### 4.1. Participant Dispositions

The number of subjects screened, screen failures, number of subjects who completed or discontinued from the study and the reasons for discontinuation will be summarized based on the safety population.

### 4.2. Protocol Deviation

All major protocol deviations will be summarized for the safety population. A listing of protocol deviations will be presented for the safety population.

All major protocol deviations will be identified and documented by PTC team prior to database lock.

### 4.3. Demographic and Baseline Characteristics

Demographics and baseline characteristics including age, sex, race, ethnicity, region, country, height, weight, and body mass index (BMI) will be summarized for safety population.

### 4.4. Medical History

Medical history will be coded with the Medical Dictionary for Regulatory Activities (MedDRA, version 26.0). Medical history records will be summarized for the safety population.

A by-subject data listing of medical history will be provided.

### 4.5. Concomitant Medications

All investigator terms for medications recorded on the case report form (CRF) will be coded using the World Health Organization (WHO) Drug Dictionary (Version B3 Mar 2025).

Prior medications will be defined as medications started prior to the first dose of study drug. Concomitant medications will be defined as medications (other than the study drug) that (1) started before the first dose of study drug and were continuing at the time of the first dose of study drug, or (2) started on or after the date of the first dose of study drug.

Any medication with partial or missing end date in which the concomitant medication status cannot be determined will be considered as a concomitant medication.

Prior and concomitant medication will be summarized as following for the safety population:

- Number and percentage of subjects with at least one concomitant medications.
- By Anatomical Therapeutic Chemical (ATC) level 2 and preferred term (PT).

A by-subject data listing of all concomitant medications will be generated.

### 4.6. Duration of Treatment with Study Drug

Duration of treatment with study drug will be calculated as number of days from the date of the first dose in PTC743-CNS-005-LSEP to the date of the last dose, inclusive.

Duration of treatment will be summarized for safety population and will also be summarized by the following categories.

- <6 months
- $\geq 6$  to <12 months
- $\geq 12$  to <18 months
- $\geq 18$  to <24 months
- $\geq 24$  to <30 months
- $\geq 30$  months

#### **4.7. Study Drug Accountability**

A by-subject data listing of study drug accountability, dose modification and medication error details will be provided.

## 5. PRIMARY ANALYSES

All primary analysis will be based on the safety population. Descriptive summaries will be based on nominal visits.

### 5.1. Adverse Events

The AE verbatim descriptions (investigator terms from the CRF) will be classified into medical terminology using the MedDRA. AEs will be coded by System Organ Class (SOC) and Preferred Term (PT) using MedDRA, Version 26.0.

Only treatment-emergent AEs (TEAEs) will be included in summary tables. All AEs will be presented in subject data listings.

#### 5.1.1. Treatment Emergent Adverse Event

A TEAE is defined as an AE that had an onset date on or after the first dose of study drug but prior to 30 days after last dose or it occurs prior to first dose of study drug and worsens in severity after first dose of study drug.

AEs with missing or partial onset date and cannot be determined if it occurred prior to the first dose of study treatment will be counted as TEAEs.

An overview TEAE table, including number and percentage of subjects with TEAEs, TEAEs by maximum CTCAE grade, treatment related TEAE, treatment related TEAE by maximum CTCAE grade, treatment-emergent SAEs (TESAEs), treatment related TESAEs, and TEAEs leading to study discontinuation will be provided.

Summary information (the number and percentage of subjects) will be tabulated for:

- Incidence of TEAEs by SOC and PT
- Incidence of TEAEs by PT in descending order
- Incidence of treatment-related TEAEs by SOC and PT
- Incidence of TEAEs by SOC, PT, and maximum CTCAE grade
- Incidence of TEAEs by SOC, PT, and relationship to study drug

TEAE tables will be sorted by SOC and then PT in decreasing frequency of the number and percentage of subjects in total column.

A by-subject data listing will be provided for all AEs.

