### 1.1. Study Design

This is an open-label, Phase 3, safety study of vatiquinone in subjects with inherited mitochondrial disease who either participated in a previous clinical study or treatment plan (rollover subjects) or failed to meet study entry criteria in a prior vatiquinone clinical study (de novo subjects). A target of approximately 200 previously treated vatiquinone subjects and approximately 4 de novo subjects will be enrolled at up to approximately 40 investigational sites worldwide. De novo subjects will receive vatiquinone oral solution (100 mg/mL), up to 200 mg, administered orally or via feeding tube three times a day (TID). Rollover subjects will continue the dosing regimen from their parent study ([Figure 1](#)).

[figure not shown]
The study will include a Screening/Baseline Visit, a Treatment Period, and an End-of-Treatment Visit. For de novo subjects, the study visits will include Screening, Run-in, Baseline, Treatment Period and End-of-Treatment Visit. For subjects that will discontinue early, an Early Termination Visit will be performed 6 weeks after discontinuation.

The duration of vatiquinone treatment will be subject to the following conditions:

[figure not shown]
- The subject has the right to withdraw consent and discontinue vatiquinone at any time.
- The relevant regulatory authority and/or PTC Therapeutics (PTC) may discontinue the study at any time.
- If the subject's condition substantially worsens after initiating vatiquinone treatment in this study, the subject will be carefully evaluated by the investigator in consultation with the PTC medical monitor. The subject will be withdrawn from treatment if continuing would place the subject at risk.
- The investigator may withdraw the subject from vatiquinone treatment if, in the investigator's clinical judgment, it is not in the subject's best interest to continue.
- If the subject is unable to tolerate vatiquinone, the subject will be withdrawn from treatment.

Safety assessments for rollover subjects will be performed at Screening/Baseline and every 6 months. Safety assessments for de novo subjects will be performed at screening, baseline, months 1, 3, 6, and 12, and every 6 months thereafter. Safety assessments will also be collected for all subjects at the End-of-Treatment Visit. Detailed schedule of activities are described in [Table 2](#), [Table 3](#), and [Table 4](#). Diagrams of the study design are provided in [Figure 1](#), [Figure 2](#), and [Figure 3](#).

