#### 5.1.2. Deaths, serious AE, and AE leading to discontinuation

The following summaries will be presented:

- Incidence of TESAEs by SOC and PT
- Incidence of treatment-related, treatment-emergent TESAEs by SOC and PT
- TEAEs leading to discontinuation by SOC and PT

Subjects who die, who have SAE and AE leading to discontinuation during the study will be provided in three separate data listings.

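### An adverse event that began before rollover and turns serious or leads to discontinuation in this study at an unchanged grade is left out of the SAE and discontinuation tables

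*SAP*

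**What the plan says.** The definition in SAP 5.1.1 has two limbs and a default:

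- **Onset limb:** "A TEAE is defined as an AE that had an onset date on or after the first dose of study drug but prior to 30" (the number is the length in days of the window that follows the final dose).
- **Earlier-onset limb:** an event also qualifies if "it occurs prior to first dose of study drug and worsens in severity after first dose of study drug".
- **Default:** "AEs with missing or partial onset date and cannot be determined if it occurred prior to the first dose of study treatment will be counted"; in other words, such events are taken to be treatment-emergent.

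Section 5.1 then states: "Only treatment-emergent AEs (TEAEs) will be included in summary tables". The summaries in 5.1.2 follow suit. The two SAE tables cover treatment-emergent SAEs only, and the discontinuation table is "TEAEs leading to discontinuation by SOC and PT". Below them, 5.1.2 plans three listings (deaths, SAEs, AEs leading to discontinuation) that carry no treatment-emergent restriction.

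On the population, section 1.1 says: "A target of approximately 200 previously treated vatiquinone subjects and approximately 4 de novo subjects will be enrolled". Rollover subjects keep the regimen of their parent study. In section 4.1, "the reasons for discontinuation will be summarized based on the safety population".

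**The concern.** An onset-or-worsening rule fits subjects who arrive untreated: whatever is present before the first dose is background unless it gets worse. Here nearly everyone arrives on treatment, so the period before the first dose in this study is largely a period on vatiquinone. An event that began then is handled as if it had preceded exposure. The only way back into the tables is a rise in severity; becoming serious or leading to discontinuation is not a trigger.

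Safety is the only primary objective, and AEs and SAEs are primary endpoints. Section 1.1 provides for withdrawal of a subject who cannot tolerate vatiquinone. Intolerance that starts in the parent study and ends in withdrawal here, without a change of grade, is an event that a reader would expect to find in the discontinuation table. Any undercount runs in one direction, towards fewer SAEs and fewer AE discontinuations.

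**Working it through.** The SAP gives no figure on this point and has no formal sample-size calculation, so the check is to apply the rule to cases.

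**Inputs**

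- TEAE rule: 5.1.1. Severity is read as CTCAE grade, because the tables there are of "TEAEs by maximum CTCAE grade".
- First-dose anchor: 5.1.1 refers to the first dose of study drug without naming the study. Section 3.1 (baseline) and section 4.6 (duration of treatment) both tie first dose to PTC743-CNS-005-LSEP, so Day 1 is taken as first dose in this study.
- Continuity of treatment: section 1.1. In addition, for subjects from Study MIT-E, footnote a of Table 2 makes the Screening/Baseline Visit the same visit as Week 72 of that study, which implies little or no gap off drug.

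**Rule as a test**

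TEAE = (Day 1 ≤ onset < last dose + 30 days), or (onset < Day 1 and grade rises), or (onset cannot be determined).

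**Cases** (illustrative: early onset 60 days before Day 1, last dose on Day 500)

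| Case | Rule as written | First-ever vatiquinone dose as anchor (set at Day −500) | With the fix below, in SAE or discontinuation tables |
|---|---|---|---|
| Early onset, becomes serious, same grade | not a TEAE | TEAE | included |
| Early onset, leads to discontinuation, same grade | not a TEAE | TEAE | included |
| Early onset, grade rises, serious or leads to discontinuation | TEAE | TEAE | included |
| Early onset, unchanged and not serious | not a TEAE | TEAE | not included |
| Onset Day 100, serious | TEAE | TEAE | included |

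An event of undeterminable onset is a TEAE as written.

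The first two rows are the gap. Those events are absent from the AE, SAE and discontinuation tables but present in the 5.1.2 listings. The third column shows that the result depends on the anchor. Sections 3.1 and 4.6 do not support the first-ever-dose reading, but 5.1.1 does not exclude it.

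**Scale**

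- Share of the target already treated: 200/204 = 98%.
- Effect of one omitted subject on a table percentage: 1/204 = 0.49 points.
- For assumed counts of 2, 5 and 10 omitted subjects: 2/204 = 0.98, 5/204 = 2.45 and 10/204 = 4.90 points.

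These counts only show the scale. The SAP gives no number of events ongoing at entry and no rate at which they turn serious or lead to discontinuation.

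**The case against.** Onset-or-worsening is a standard definition, and in an extension study it keeps parent-study events from being counted twice. The study is open-label and descriptive, with no hypothesis test. The affected events are not lost: all AEs are listed, and 5.1.2 has dedicated listings for SAEs and for AEs leading to discontinuation. For a handful of cases, subject-level listings are informative. The protocol or CRF, not shown here, may record a change to serious as a new event with a new onset date, which would make it a TEAE. Section 4.1 names no reason categories, so a mismatch with disposition is not certain.

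Much of this stands and limits the point. It does not remove it. Avoiding double counting is a reason to keep unchanged, non-serious carry-over events out of the tables. It is weaker for an event whose seriousness or consequence arises in this study. A new-record convention for serious events would not by itself cover discontinuation at an unchanged grade. The tables and listings of 5.1.2 have different scopes, and the SAP gives no rule to reconcile them.

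A reader might infer more than the SAP supports:

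- **That these events go unreported.** They do not; the listings carry them.
- **That the counts are biased by a known amount, for example a fifth of the discontinuation table.** That needs assumed numerators and denominators that the SAP does not contain.
- **That the SAP needs a separate table of events ongoing at entry, or a changed death summary.** The first depends on onset and first-dose dates from parent studies and treatment plans whose availability is uncertain. The SAP has a death listing but no death table to amend.

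**Conclusion.** The point holds as a possible one-directional undercount in the SAE and AE-discontinuation tables. It rests on three conditions: first dose means first dose in this study (inferred from 3.1 and 4.6), the grade does not rise, and, for serious events, the change to serious is not recorded as a new AE. Where such an event occurs, the tables will not match the 5.1.2 listings. If adverse event is a reason category in 4.1, they may not match the disposition summary either. The number of subjects affected cannot be derived; each is worth about 0.5 percentage points of 204. That is small in absolute terms, but it matters more where few subjects have the event. The change is worth making before database lock because it concerns a primary safety result and the events must be identified for the listings anyway.

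**What to change.** 1. In 5.1.1, state that first dose means first dose in PTC743-CNS-005-LSEP.
2. In 5.1.1 and 5.1.2, include in the SAE and discontinuation summaries (the overview table and the tables by SOC and PT) every AE that becomes serious or leads to discontinuation on or after that dose and within the existing post-dose window, whatever its onset date and whether or not its grade changed. Flag those with onset before Day 1.

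The general TEAE incidence tables can keep the present rule, so unchanged carry-over events are still not counted again.

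**Cost:** a few sentences in the SAP, a flag in the table programs, and the date on which each early-onset event became serious or led to discontinuation. The listings already require these events to be identified. The downside is a few more subjects in those tables, some with events already reported in a parent study; the flag lets the reader separate them.

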## APPENDIX 1. SCHEDULE OF EVENTS

**Table 2:** Schedule of Assessments – Rollover Subjects

Study Period	Screening/Baseline a	Treatment		EOT Visit	ET (6 Weeks After D/C) b
Study Month	Day 1	Telephone Visits 3 Months (84±7 Days) After On-Site Visits	Every 6 Months (168±7 Days)		
Informed consent	X c				
Demographics	X				
Medical history	X				
Vital signs	X		X	X	X
Height	X				
Weight	X	X d	X	X	X
Physical examination	X		X	X	X
12-Lead ECG	X		X	X	X
Urine pregnancy test (WOCBP) l	X		X	X e	X
Hematology (CBC w/ differential)	X m		X m	X m	X m
Serum chemistry	X m		X m	X m	X m
Coagulation panel	X m		X m	X m	X m
Urinalysis f	X		X	X	X
NPMDS g	X		X	X	X
CarerQoL-7D g	X h		X	X	X
PedsQL g	X h		X	X	X
Drug dispensed i	X	X	X		
Pre-/post-shipment contact j		X			
Drug compliance k			X	X	X
AE/SAE assessment	X	X d	X	X	X
Prior/concomitant medication	X	X d	X	X	X

**Abbreviations:** AE, adverse event; CBC, complete blood count; D/C, discontinuation; ECG, electrocardiogram; EOT, End-of-Treatment; ET, Early Termination; NPMDS, Newcastle Pediatric Mitochondrial Disease Scale; PedsQL, Pediatric Quality of Life Inventory™; SAE, serious adverse event; Study MIT-E, Study PTC743-MIT-001-EP; WOCBP, women of childbearing potential

a On-site visit applicable to all subjects rolling over to this study. For subjects rolling over from Study MIT-E, the Screening/Baseline Visit in this study will also be the Week 72 visit in Study MIT-E.

b Subjects who discontinue vatiquinone prematurely should complete an ET Visit.

c Informed consent will be signed before any study procedures. In case the subject/caregivers cannot attend the Screening/Baseline Visit in the clinic, remote consenting can be obtained.

d Clinical site staff will contact subject or parent(s)/legal guardian(s) every 3 months (by telephone if there is no clinic visit) to assess AEs, weight, and concomitant medications.

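### The 30-day post-dose limit in the TEAE definition applies to new-onset events but not to worsening of events present before the first dose

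*SAP*

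**What the plan says.** SAP section 5.1.1 joins two limbs with an 'or'. The first covers "an AE that had an onset date on or after the first dose of study drug but prior to 30 days after last dose". The second covers an event for which "it occurs prior to first dose of study drug and worsens in severity after first dose of study drug". The 30-day limit belongs to the onset date in the first limb. The second limb sets no upper limit on the date of worsening, and no other section of the SAP supplies one.

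The flag decides what is tabulated. Section 5.1 states: "Only treatment-emergent AEs (TEAEs) will be included in summary tables". All AEs, treatment-emergent or not, go into the subject listings. Section 1.3.1 names AEs and SAEs among the primary endpoints.

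On follow-up after stopping, section 1.1 says that for early discontinuers "an Early Termination Visit will be performed 6 weeks after discontinuation". Tables 2, 3 and 4 in Appendix 1 all mark AE/SAE assessment at that visit.

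**The concern.** The two limbs should answer one question: did something new or worse happen while the subject was on drug or within a fixed time after it? As written, they answer it over different periods. The 30-day limit cannot be carried over to the second limb by reading, because it is attached to the onset date, and in the second limb the onset is by definition before the first dose.

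The SAP's own schedule makes the gap reachable, since AE information is collected after day 30 off drug. Two events on the same off-drug day can then be classified in opposite ways, one tabulated and the other only listed, and the SAP gives no reason for the difference. What is at stake is the consistency of the incidence counts in the primary safety tables. Unless the text is changed, the programmer must either follow the uneven rule literally or add an unstated limit.

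**Working it through.** The SAP gives no figure to reproduce here, and section 1.4 says the sample size rests on no formal hypothesis. The check codes the two limbs as written and compares them day by day.

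Inputs:
- d = date of the event or worsening minus the date of the last dose, in days.
- Limb 1 (section 5.1.1): onset on or after the first dose and d < 30. The wording is strict, so day 30 itself is outside.
- Limb 2 (section 5.1.1): onset before the first dose and worsening after it, with no condition on d.
- Last scheduled AE assessment for early discontinuers (section 1.1; Tables 2 to 4): 6 weeks × 7 = 42 days after discontinuation.
- Assumption: the discontinuation date equals the last-dose date. The SAP does not say so.

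Results for an event that starts, or first worsens, on day d:

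| d | New event a TEAE? | Pre-dose event first worsening a TEAE? | Same, with the limit d < 30 added |
|---|---|---|---|
| 0 | yes | yes | yes |
| 29 | yes | yes | yes |
| 30 | no | yes | no |
| 35 | no | yes | no |
| 42 | no | yes | no |
| 60 | no | yes | no |

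The limbs agree on days 0 to 29 and disagree from day 30 on. Up to the Early Termination Visit the discordant days are 30 to 42, which is 42 − 30 + 1 = 13 days. Any AE record later than that is also discordant, because limb 2 never closes. With the same limit placed on the worsening date, the two limbs agree on every day checked.

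The number of affected events cannot be derived. It would need the number of early discontinuers, how many of them have an AE recorded before the first dose, and how many of those AEs first worsen in this interval. The SAP gives none of these.

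**The case against.** The strongest case on the other side concerns reach, not the text.

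- **Several conditions must coincide.** The subject needs an AE recorded before the first dose, an early discontinuation, no worsening on treatment or in the first 30 days off drug, and then a first worsening within about 13 days. An event that had already worsened earlier is a TEAE in any case. This stands, and it is why the effect is probably small.
- **Few subjects have a real pre-dose AE period.** For rollover subjects, Screening/Baseline is a single Day 1 visit at which medical history is also taken. Conditions carried over from the parent study may be recorded as medical history, and a later worsening might then be a new AE with its own onset, governed by limb 1. Only de novo subjects, about 4 planned, have a screening and run-in period of up to 42 days. This largely stands. The SAP does not state the recording convention, so it does not close the gap. Nor does the document support inferring that many rollover subjects are affected because their disease is progressive.
- **The error is inclusive.** The study has no comparator arm and no hypothesis test, and all AEs are listed. The uneven rule can only add events to the tables and hides none. This stands, but a rule that is inclusive for one kind of event and not for the other is still inconsistent.

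Four stronger readings are tempting, and the document does not support them.

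- A reader might infer that such an event enters every AE table. It enters the serious-event tables only if serious, and the treatment-related tables only if judged related.
- A reader might infer that the event is thereby attributed to the drug. The TEAE flag is a matter of timing, and relationship to study drug is tabulated separately.
- A reader might size the problem as off-drug person-time, for example 100 × 13/365.25 = 3.6 person-years per 100 early discontinuers. That counts the time of all discontinuers, not only those with a pre-dose AE that has not yet worsened, so it says nothing about the number of events.
- A reader might infer that the missing-date rule, which treats events of uncertain onset as treatment-emergent, has the same defect. It says: "AEs with missing or partial onset date and cannot be determined if it occurred prior to the first dose of study treatment will be counted". A date whose known part places it after the post-dose cut-off is also known to be after the first dose, so that rule is not triggered and limb 1 already excludes the event. What remains is a partial date that is clearly after the first dose but straddles the cut-off. That is a narrow and separate matter.

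**Conclusion.** The point holds in a limited form. From day 30 after the last dose, section 5.1.1 classifies a first worsening of a pre-dose event as treatment-emergent and a new event on the same day as not. Scheduled AE assessment makes this observable for about 13 days (days 30 to 42) in each early discontinuer, assuming that discontinuation coincides with the last dose. The direction is toward over-counting TEAEs. The size is probably small and cannot be estimated from the document.

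This is a rule that the SAP states and sets unevenly, not a detail that it leaves to the protocol. It deserves correction because the flag controls the primary AE tables and the correction is nearly free. It does not call the overall safety conclusions into question.

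**What to change.** Apply one post-dose cut-off to both limbs in section 5.1.1. The second limb could read: *or started before the first dose and worsened in severity on or after the first dose and before the same post-dose cut-off*. Its starting point then also matches that of the first limb. Whatever cut-off is kept for new events, the second limb will follow it. The missing-date rule needs no change for this purpose.

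The cost is one clause in the SAP and one condition in the program that derives the TEAE flag. The TEAE count may fall slightly. Any event that drops out of the tables remains in the by-subject AE listing, so no information is lost.
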